6.2 Consolidation Chemotherapy

6.21 Patients who have received consolidation treatment prior to coming to City of Hope will be evaluated to determine how many doses of HD Ara-c and anthracycline they have received. Patients who have received more than 200mg/m² of anthracycline will not receive idarubicin. Patients who have received 8 or more doses of HD Ara-c will have GCSF primed cells collected. Patients who have had < 8 doses of HD Ara-C will receive additional HD Ara-C not to exceed 12 doses [36grams/m²].

6.22 Patients who have received no consolidation treatment will follow the following treatment plan:

Revised 8/7/00

a). Beginning 4 hours prior to starting Ara-C all patients will be adequately hydrated. All patients will require anti-emetics to control nausea and vomiting. Patients will undergo a neurological assessment prior to each dose of Ara-C for evaluation of cerebellar symptoms.

Revised 8/7/00

b) Patients will receive Ara-C 3 gm/m² IV over 3 hours every 12 hours for a total of 8 doses. (Day 1-4). Patients age 55 to 60 will receive 2gm/m² of Ara-C.

Revised 5/4/01

c) Idarubicin 12 mg/m² will be given by slow intravenous infusion (5-10 minutes) after Ara-C dose 1, 3, 5. (Day 1-3). Patients with good risk cytogenetics (t 8;21) or inv 16 or (t 16;16) will not receive the idarubicin.

Revised 3/11/02

d) GCSF 10 µg/kg IV or subcutaneously in 2 divided doses will be started 7 days after Ara-C completed and continued until peripheral stem cell collections are completed.

e) Once patients' WBC >5000/µl peripheral stem cells will be collected with the goal collecting 3 x 10⁶/kg CD34 cells (target 3-5 x 10⁶/kg). If stem cell collections are poor the stem cell collection should then be delayed until the platelet count recovers to > 50,000. The G-CSF

dose can be increased to 16 mcg/kg/day subcutaneously in 2 divided doses [or I/V depending on transplant center standard protocol.

Revised 8/7/00

f) CBC, platelet count daily, (differentials per MD discretion), comprehensive metabolic panel plus uric acid, LDH, phosphorous and cholesterol, Mg⁺⁺ are drawn daily during chemotherapy then every Monday, Wednesday, Friday during consolidation therapy.

6.3 Dose Adjustments

a) Idarubicin	Total Bilirubin	Dose Reduction
	< 2.5	0
	> 2.5 <5	50%
	>5	100%
b) Ara-C	Creatinine	Dose Reduction
	< 1.3	0
	1.3 – 1.4	33%
	1.5 – 2.0	66%
	> 2.0	Hold Dose

For any dose adjustment reduction an attempt will be made to give a total Ara-C dose of 24 gm/m², i.e. give difference on day 5 and 6. No dose should exceed 3gm/m².

6.31 Supportive Care:

Revised 8/7/00

- a) Decadron eye drops are given throughout the treatment with Ara-C and should be continued for four days following the completion of Ara-C.
- b) All patients will have a right atrial catheter inserted prior to beginning or during the consolidation chemotherapy.
- c) All patients will receive systemic fungal prophylaxis with Amphotericin B (0.15 mg/kg/d), liposomal Amphotericin B or Itraconazole 200 mg b.i.d. following completion of chemotherapy until normalization of ANC's.
- d) All patients will receive filtered and irradiated (2500 cGy) blood products. Platelet and red cell transfusions will be given as clinically indicated.
- e) All patients should receive hyper alimentation until oral caloric intake is adequate to meet the patients nutritional needs.

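### The Ara-C make-up target of 24 g/m² in section 6.3 is 50% above the planned course total for patients aged 55 to 60

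*Combined protocol and SAP*

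**What the plan says.** Section 6.22(b) gives Ara-C at 3 g/m² "IV over 3 hours every 12 hours for a total of 8 doses" on days 1 to 4. It then lowers the dose for the oldest patients: "Patients age 55 to 60 will receive 2gm" per m². It states no different number of doses for them. Section 5.0(a) admits patients up to the 61st birthday, so this age group is within the trial.

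Section 6.3 reduces Ara-C by creatinine: no reduction below 1.3, 33% at 1.3 to 1.4, 66% at 1.5 to 2.0, and hold above 2.0. It then adds: "For any dose adjustment reduction an attempt will be made to give a total Ara-C dose of 24 gm" per m², "i.e. give difference on day 5 and 6", and "No dose should exceed 3gm" per m². The rule covers every reduction. No age exception appears in 6.3 or elsewhere.

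Section 6.21 covers patients who arrive with prior consolidation. Those with fewer than 8 doses of high-dose Ara-C "will receive additional HD Ara-C not to exceed 12 doses", with 36 g/m² given in brackets. Section 6.3 does not say how its total applies to them.

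**The concern.** The printed target fits a patient planned for 8 doses of 3 g/m². For a patient aged 55 to 60 it exceeds what would have been given with no reduction at all. The renal-safety rule therefore points upward in the age group that 6.22(b) chose to dose lower. A patient with normal creatinine is planned for 16 g/m², while the same patient after a creatinine rise has a target of 24 g/m².

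What is at stake is dosing safety. Section 4.14 lists ataxia and encephalopathy among the toxicities of Ara-C, and 6.22(a) requires a cerebellar assessment before each dose.

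**Working it through.** **Inputs.** 3 g/m² × 8 doses, and 2 g/m² per dose at ages 55 to 60 (6.22(b)). Reductions of 33% and 66%, target 24 g/m², ceiling 3 g/m² per dose, make-up on days 5 and 6 (6.3). Limit of 12 doses or 36 g/m² (6.21).

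**Assumptions.** Patients aged 55 to 60 receive the same 8 doses. Days 5 and 6 offer four slots if the 12-hour interval is kept. Make-up doses stay at the 2 g/m² age dose, or at its reduced value while a cut persists.

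**The plan's own figure.** Planned total = dose × number of doses = 3 × 8 = 24 g/m², which reproduces 6.3 exactly.

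**Ages 55 to 60.** Planned total = 2 × 8 = 16 g/m². Excess of the target = 24 − 16 = 8 g/m², and 8/16 = 50%.

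**One dose cut by 33%.** Given on days 1 to 4 = 7 × 2 + 2 × 0.67 = 15.34 g/m². Withheld = 16 − 15.34 = 0.66 g/m². Gap to the printed target = 24 − 15.34 = 8.66 g/m².

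**What could be reached with four slots.** A full make-up dose is 2 g/m². A dose cut by 33% is 1.34 g/m², and one cut by 66% is 0.68 g/m². No row reaches 24 g/m², so all four slots are used.

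| Pattern of reduction | Days 1–4 (g/m²) | Days 5–6 (g/m²) | Total (g/m²) | % of 16 |
|---|---|---|---|---|
| One dose cut 33%, then recovered | 15.34 | 4 × 2 = 8.00 | 23.34 | 146% |
| One dose cut 66%, then recovered | 14.68 | 8.00 | 22.68 | 142% |
| One dose held, then recovered | 14.00 | 8.00 | 22.00 | 137.5% |
| 33% cut from dose 8, persisting | 15.34 | 4 × 1.34 = 5.36 | 20.70 | 129% |
| 33% cut from dose 5, persisting | 8 + 5.36 = 13.36 | 5.36 | 18.72 | 117% |
| 33% cut from dose 1, persisting | 8 × 1.34 = 10.72 | 5.36 | 16.08 | 100.5% |
| 66% cut from dose 1, persisting | 8 × 0.68 = 5.44 | 4 × 0.68 = 2.72 | 8.16 | 51% |

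With only two slots (one dose per day), one 33% cut followed by recovery gives 15.34 + 2 × 2 = 19.34 g/m² (121%). The overshoot is largest when the creatinine rise is brief or mild.

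**Patients under 6.21.** Assume k prior doses of 3 g/m², a target that does not count them, and a 12-dose limit that does. The cumulative amount is then 3k + 24. For k = 1 to 4 this is 27, 30, 33 and 36 g/m², within the limit. For k = 5 to 7 it is 39, 42 and 45 g/m², above it. If exactly 8 further doses of 3 g/m² are planned, 24 g/m² is the right total. The implied dose is 36/12 = 3 g/m², so the per-dose ceiling fits these patients when they are under 55.

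**The case against.** The best defence is that 6.3 means something milder than its number. It speaks of giving the difference and of making an attempt, which suggests restoring what was withheld. The lower age dose is an assigned dose, not a reduction under 6.3. The literal reading also has the perverse result of giving more drug to the patient with the worse kidneys. This is probably the intent. But the sentence defines the difference by reference to a total, and the only total printed is 24 g/m². A dosing instruction should not depend on the reader rejecting its figure.

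Safeguards also exist. Entry requires creatinine clearance above 60 ml/min, and the creatinine table applies to every dose. Under 6.22(a), "Patients will undergo a neurological assessment prior to each dose of Ara-C for evaluation of cerebellar symptoms". Under 6.22(f), the panels "are drawn daily during chemotherapy then every Monday, Wednesday, Friday during consolidation therapy". These can limit or stop a dose, but none corrects the target, and once creatinine is below 1.3 the table allows the full dose again.

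Three stronger readings are tempting, and the documents do not support them:

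- A reader might infer that the 3 g/m² ceiling raises the dose for ages 55 to 60, so that 24 g/m² is actually reached at 8.66/4 = 2.17 g/m² per make-up dose. It is only a ceiling. It does not override the 2 g/m² in 6.22(b), and a 2 g/m² dose satisfies both.
- A reader might infer that the total is equally wrong for patients under 6.21. The number of additional doses is not fixed there, and 6.3 does not say whether prior doses count. For them the total is ambiguous, not shown to be wrong.
- A reader might infer from Appendix III that creatinine goes unchecked on a make-up day. Section 6.22(f) already requires daily panels during chemotherapy, and the appendix grid may have been distorted when the text was extracted.

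**Conclusion.** The point holds for ages 55 to 60: the target printed in 6.3 is 24 g/m² against a planned 16 g/m², an excess of 8 g/m² or 50%. That rests only on the same 8 doses applying to this age group, and 6.22(b) states no other number.

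The dose actually reached depends on assumptions the protocol does not settle. With four slots and make-up doses held to 2 g/m², it is at most 23.34 g/m² (146% of plan), after a single 33% cut that resolves at once. It falls to about the planned total, or below it, when cuts are early and persistent. The documents do not say how many patients would be affected. This is a wording error in a dosing rule that should be corrected, and it leaves every endpoint, the sample size and the stopping rules as they are.

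**What to change.** Reword the make-up sentence in 6.3 to say three things:

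- Make-up on days 5 and 6 restores no more than the amount withheld from the patient's own planned course total: 24 g/m², or 16 g/m² for ages 55 to 60.
- Each make-up dose is no larger than the patient's assigned dose: 3 g/m², or 2 g/m² for ages 55 to 60.
- Each make-up dose remains subject to the creatinine table.

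For patients under 6.21, the same sentence should say that make-up restores only what was withheld from their additional doses and stays within the 12-dose (36 g/m²) limit. In the example of one 33% cut at ages 55 to 60, make-up would then be 0.66 g/m² and the total 15.34 + 0.66 = 16 g/m². The sponsor's clinicians should confirm the values. The cost is one reworded sentence, with no added assessments and no change to the analysis.

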6.4 Cryopreservation of Peripheral Blood Stem Cells

At least 3×10^6 CD34 positive cells/kg will be collected with a target range of 3 to 5×10^6 CD34⁺ cells/kg. Enriched mononuclear cells/CD34 preparation is

obtained by peripheral blood apheresis. Cells are cryopreserved according to participating site institutional standard operating procedure after review and approval of the P.I. ([name].) and the City of Hope Stem Cell lab director ([name], [contact] [name], [contact]).

6.5 High Dose Therapy Treatment

Revised 8/7/00

6.51 Pre-Transplant Evaluation: Within 4 weeks of starting busulfan.

- a) Prior to admission patient will have a complete history and physical examination performed. Special attention will be given to prior chemotherapy, height, weight, and body surface area should also be noted.

Rev. 11/7/01

Revised 8/7/00

- b) CBC with differential, platelet count, comprehensive metabolic panel.

Revised 3/11/02

- c) Chest x-ray

- d) MUGA scan or 2D-Echocardiogram.

Revised 8/7/00

- e). Bone marrow aspirate and biopsy, and cytogenetics needs to be done within four weeks of starting busulfan.

Rev. 11/7/01

The following pre-study tests should be obtained within 4 weeks of starting treatment in accordance with good medical practice. Results of these tests do not determine eligibility and minor deviations are acceptable if they do not impact on patient safety in the clinical judgement of the treating physician. The Study Coordinator must be contacted if there are significant deviations in the values of these tests.

- f). Uric acid, LDH, phosphorous, cholesterol, magnesium, urine analysis, herpes simplex titer, CMV titer, immunoglobulin levels, thyroid panel (free T4 and TSH), chest x-ray and EKG, HLA typing of patient and siblings.

- g). PFT's as indicated.

Patients who are evaluated at transplant center after already receiving consolidation therapy are required to have the same tests performed pre consolidation treatment. (6.1 a-g)

*If patients tests are performed and the transplant is delayed due to non medical causes [e.g. insurance] and patient receives no further treatment then echocardiogram, PFT's, chest x-ray and antibody titres do not need to be repeated within 3 months.

6.52 Preparative Chemotherapy Regimen:

Rev. 11/7/01

Version 09
4/20/04

Friday/Day –17

Begin Dilantin 300mg p.o. t.i.d. x 1 day , then 300mg p.o./I/V daily x 13 days.

Tuesday/Day –13

Admission or outpatient, dilantin blood levels will be checked and dose adjusted as needed to meet therapeutic range. Further adjustments if clinically indicated. Busulfan test dose administered over 2 hours as a single dose. The I/V dose is calculated as follows:

1. Body surface area (BSA) is calculated by the equation:

$$\text{BSA} = \frac{(\text{Actual body wt.}(\text{kg}) \times \text{height}(\text{cm}))}{3600}$$

2. Dose of IV busulfan that is equivalent to a total dose of 11mg/kg of the oral dose is: 22 mg/m^2 per dose. Blood levels will be obtained with the first dose as per appendix 1. Busulfan levels will be performed at COH ([name], City of Hope National Medical Center, [name] and will only be sent to Quest Diagnostics as a back-up. Call [name] [contact] 24hrs before shipping samples.

Wednesday/Day –12

Busulfan AUC will be calculated by standard methods available in the City of Hope Analytical Pharmacology Core Facility (APCF). The resulting AUC will be used to determine the dose required to achieve an AUC of $800 \mu\text{M}^* \text{ min}$ according to the following formula:

$$\text{Adj dose} = \text{Current dose} \times \frac{800 \mu\text{M}^* \text{ min}}{\text{test dose AUC}}$$

The maximum dose given will not exceed 32 mg/m^2 . There is no limit on dose reduction Busulfan dose will only be adjusted for AUC's <700 or $>900 \mu\text{M}^* \text{ min}$.

Revised 8/7/00

Thursday/Day –11

If the adjusted dose of busulfan is indicated, the adjusted dose will be given and blood levels will be repeated. Further dose adjustments will be performed if $\text{AUC} > 1000$.

Friday/Day –10

Patient admitted to BMT or outpatient department to receive further doses of Busulfan. Resume busulfan once PK results are known.

Revised 8/7/00

Busulfan dose is resumed and is repeated every 6 hours for a total of 16 doses (including test dose(s). Last dose is given at midnight on day –7.

Tuesday/Day-6

Fractionated TBI will be given at 120 cGy per fraction for a total of 4 days [day –6, -5, -4, -3] for a total of 10 fractions for a total dose of 1200cGy. Or FTBI will be given at 150cGy per fraction x 8 fractions for a total of 4 days (-6,-5, -4,-3) total dose 1200 cGy Appendix IIa.

Saturday/Day –2

VP-16 30mg/kg based on adjusted ideal body weight will be administered.

CALCULATIONS OF IDEAL BODY WEIGHT

1. Male IBW = 50kg + 2.3 kg(height [in] - 60)
2. Female IBW = 45.5 kg + 2.3kg (height [in] - 60)

Sunday/Day –1

Rest

Monday/Day 0

The frozen peripheral blood cells will be transported to the transplant unit and thawed in a water bath outside the patient's room. Each bag will be infused undiluted rapidly through standard IV tubing without a filter. *Premeds for stem cell infusion will be given as per the standard operating procedure of the respective transplant center. A recommended regimen is hydrocortisone and 25mg of diphenhydramine and Mannitol 12.5gm per MD discretion. Those patients who have $\geq 3 \times 10^6$ CD34 cells/kg PSC's will receive PSC's only. All other patients will receive both primed PSC's and bone marrow.

Revised 3/11/02

Saturday/Day +5

Start GCSF 5 μ g/kg IV or subcutaneously.

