Due to the long hematological recovery and no literature evidence for adding idarubicin to the consolidation treatment, the protocol will be amended to omit idarubicin for patients with good risk cytogenetics.

At City of Hope between 8/92 and 10/98 61 patients were entered on a phase I study of escalating doses of busulfan in combination with TBI and VP-16 in patients with advanced hematological malignancies in an effort to try and improve the outcome of allogeneic bone marrow transplant in these poor risk patients. The MTD was defined at 11 mg/kg of busulfan in combination with FTBI 1200 cGy and VP-16 60mg/kg. The median AUC was 892 μ M*min (460-1267) for this group of patients. With a median follow up of 11.5 months, the disease free survival is 32%, and the probability of relapse is 40%. The only variable predictive of an improved disease free survival + relapse was Busulfan dose of 7-8mg/kg. An AUC of 700-950 μ M*min demonstrated a trend to a decreased relapse rate and improved DFS.

Allogeneic and autologous BMT studies performed in approximately 100 patients the I/V formulation has been shown to have more predictable pharmacokinetic properties than the oral preparation resulting in a better toxicity profile.⁽²⁶⁻²⁸⁾

Relapse is still the major reason for failure for BMT. In an attempt to try and decrease the relapse rate post autologous stem cell transplant we plan to substitute intravenous busulfan for cyclophosphamide in the conditioning regimen.

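### The BSA equation for the busulfan test dose (section 6.52) has no square root in the supplied text; taken literally it inflates that one dose about 1.5- to 2.3-fold

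*Combined protocol and SAP*

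**What the plan says.** Section 6.52, Day -13, item 1 states: "Body surface area (BSA) is calculated by the equation". The equation that follows divides the product of actual body weight in kg and height in cm by 3600. The supplied text shows no radical or exponent, and the document has no other BSA formula.

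Item 2 sets the dose: "Dose of IV busulfan that is equivalent to a total dose of 11mg/kg of the oral dose is" 22 mg/m² per dose. This is the Day -13 test dose.

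On Day -12 the dose is rescaled by 800 divided by the test-dose AUC. The limits are: "Busulfan dose will only be adjusted for" AUCs below 700 or above 900 µM*min; "The maximum dose given will not exceed" 32 mg/m²; and no floor on reductions. The text does not say which BSA the maximum uses, or whether it reaches back to the test dose.

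For Day -11: "If the adjusted dose of busulfan is indicated, the adjusted dose will be given and blood levels will be repeated". For Day -10: "Resume busulfan once PK results are known". The course is then defined: "Busulfan dose is resumed and is repeated every 6 hours for a total of 16 doses", a count that includes the test dose or doses.

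**The concern.** Without the root, the equation gives values that cannot be adult surface areas in m², yet the next item multiplies the result by a dose per m². The test dose is the only busulfan dose set from BSA before any AUC has been measured, so nothing downstream can correct it once it is given. Sections 4.35 and 7.0 list seizures and potentially fatal liver damage among busulfan's toxicities. If the 32 mg/m² maximum is computed from the same BSA, that safeguard is loosened by the same factor. Appendix IIa shows that a second institution treats under this protocol, so the page is used for dosing by people other than its authors.

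**Working it through.** **Inputs from section 6.52.** Equation W × H / 3600; 22 mg/m² per dose; maximum 32 mg/m²; target AUC 800; no adjustment within 700–900; 16 doses including the test dose.

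**Assumed inputs.** Body sizes 50 kg/155 cm, 70 kg/170 cm and 100 kg/185 cm (the documents give none), and AUC proportional to dose.

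The plan gives no worked BSA and no dose in mg, so there is no figure of its own to reproduce.

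**Step 1: BSA and test dose.** Literal L = W × H / 3600. Rooted R = sqrt(W × H / 3600). Since L / R = R, the inflation factor is the rooted BSA itself.

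| Size | L | R (m²) | 22 × L (mg) | 22 × R (mg) | Factor |
|---|---|---|---|---|---|
| 50/155 | 7750/3600 = 2.15 | 1.47 | 47.4 | 32.3 | 1.47 |
| 70/170 | 11900/3600 = 3.31 | 1.82 | 72.7 | 40.0 | 1.82 |
| 100/185 | 18500/3600 = 5.14 | 2.27 | 113.1 | 49.9 | 2.27 |

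**Step 2: against the protocol's own maximum.** Per rooted m², the literal test dose is 22 × R = 32.3, 40.0 and 49.9 mg/m². All three exceed 32 mg/m².
- If the maximum covers the test dose and uses the rooted BSA, the excess stops at 32/22 = 1.45-fold.
- If the maximum uses the literal BSA, it never limits the test dose, because 22 is below 32. It then stands at 32 × L = 69, 106 and 164 mg, instead of 32 × R = 47, 58 and 73 mg.

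**Step 3: later doses.** Let A be the AUC that a patient would have at a true 22 mg/m². The literal test-dose AUC is A × R. The adjusted dose is 22 × L × 800 / (A × R) = 22 × R × 800 / A, so the BSA error cancels. Example at 70/170 with A = 800: test-dose AUC 800 × 1.818 = 1454, and adjusted dose 72.7 × 800 / 1454 = 40.0 mg, the intended dose.

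Cancellation is not complete, for two reasons.
- The range of A that escapes adjustment moves from 700–900 to 700/R–900/R: 477–613, 385–495 and 309–397 at the three sizes. A patient with A in 700–900, who should need no change, would have a test-dose AUC of at least 700 × 1.467 = 1027. That patient would therefore need an adjusted dose and repeat levels on Day -11. A patient inside the shifted range keeps the larger mg dose, but has a measured AUC of 700–900.
- A correct maximum limits upward adjustment when A is below 800 × 22/32 = 550. A loosened one does so only below 550/R = 375, 303 and 243. The AUC aimed for is still 800.

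**Step 4: share of the course.** Direct excess over 16 intended doses = (22 × L − 22 × R) / (16 × 22 × R) = (R − 1)/16.
- 50/155: 15 mg of 516 mg, 2.9%
- 70/170: 33 mg of 640 mg, 5.1%
- 100/185: 63 mg of 798 mg, 7.9%
- With the correct maximum applied to the test dose: (1.45 − 1)/16 = 2.8% at all three sizes

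**The case against.** The strongest objection is that the point depends on one glyph in a machine-read equation. Symbols are damaged elsewhere in the text; the platelet threshold in section 6.54 has lost part of its unit. A radical lost in conversion would not be an error in the plan. This stands, and it is why the source page comes first. It does not settle the matter: in the same section the conversion kept both fractions and the superscripts in mg/m².

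Second, the documents contain no internal proof. Neither form is dimensionally an area, so the case rests on implausible values such as 3.31 and 5.14, not on units. The stated equivalence to 11 mg/kg oral cannot decide it either, because no oral-to-IV factor is given. Both remarks stand.

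Third, practice offers protection. BSA is recorded at both work-ups (sections 6.1 and 6.51), and Ara-C, idarubicin and IL-2 are dosed per m² with no formula supplied. Sites therefore already have a working BSA, and a value of 3.3 would probably be noticed. This lowers the chance of harm but does not make the printed rule right.

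A reader might infer that the whole busulfan course is inflated about twofold, or that patients were in fact overdosed. The documents support neither: later doses follow measured AUC, and nothing shows that anyone applied the literal formula. Nor should expected AUCs be projected from the phase I experience in section 3.0 ("The median AUC was 892"). Those values come from escalating busulfan doses, not from IV busulfan at 22 mg/m².

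**Conclusion.** The point holds for the text as supplied, in limited form. The equation lacks a square root and, applied literally, raises the Day -13 test dose by a factor equal to the true BSA: 1.47 to 2.27 at the assumed sizes, or at most 1.45 if a correctly computed 32 mg/m² maximum governs the test dose. The direct excess is mainly one dose of 16, about 3% to 8% of the intended course. With AUC proportional to dose, later exposure stays in or returns to about the target, at the price of more Day -11 adjustments and repeat levels.

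The endpoints, sample size and stopping rules are untouched. The conclusion rests on assumed adult body sizes and on no radical being printed on the source page. It is a dosing-text error worth correcting for patient safety, with medium confidence until that page is seen.

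**What to change.** Check the source page of section 6.52. If a radical or an exponent of one half is printed, the equation needs no change. If not:

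- Replace the equation with BSA (m²) = sqrt(actual weight (kg) × height (cm) / 3600).
- State that the 32 mg/m² maximum uses this BSA and applies to every dose, including the test dose.
- Add one worked example: 70 kg and 170 cm give 1.82 m², a test dose of 40 mg and a maximum of 58 mg.

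The cost is a page check and, at most, a one-line correction with one clarifying sentence and the example. The AUC targeting scheme does not change.

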Autologous PSC Reinfusion: Side effects from the bone marrow and peripheral stem cell infusion should be minimal. Volume overload may be seen, but can be managed with diuretics. Fevers and chills may occasionally be encountered. At the University of Nebraska at least two patients developed acute abdominal pain of unknown cause during their marrow infusions. The pain was managed with narcotic analgesics and resolved spontaneously. The lysis of frozen erythrocytes may be associated with hemoglobinuria. Patients will have positive tests for blood in the urine, but no erythrocytes will be found in the sediment. At the University of Nebraska three patients developed acute renal failure after autologous bone marrow infusion. This problem was presumed to be due to hemoglobinuria and was no longer seen after red blood cells were removed from the marrow prior to cryopreservation. This is not expected to be a problem since we will also be removing the red cells with Ficoll-Hypaque. DMSO will be infused along with the bone marrow. It is excreted through the lungs and its characteristic odor may be noticeable for a few days after marrow infusion.

8.0 STATISTICAL CONSIDERATIONS:

8.1 Primary and Secondary Endpoints: The primary endpoints of this Phase II study are to evaluate the toxicity and efficacy of FTBI/VP-16 and targeted Busulfan dosage for AUC 700-900 as a preparative regimen for autologous BMT with primed peripheral stem cells following consolidation therapy with high dose Ara-c and idarubicin or high dose Ara-c alone in patients with AML in first complete remission (CR). Complete remission will be defined as neutrophils >1500/ml and platelets >100,000. Efficacy will be estimated as 2 and 5 year disease-free survival (DFS). The role of IL-2 following autologous BMT will also be evaluated based on feasibility of administration and ability to tolerate IL-2. The effect of cytogenetics, WBC at presentation, AUC of Busulfan and number of courses of induction therapy to achieve remission will be evaluated as possible prognostic factors for relapse, DFS, and overall survival.

8.2 Sample Size Estimation and Length of Accrual: A total of 50 patients with AML in first CR and less than \leq 60 years old will be accrued to this trial, so that in estimating the engraftment and relapse rates the maximum standard error will be 0.07. We expect to accrue approximately 10-12 patients per year so that this trial will require 4-5 years for completion.

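### Day 0 orders bone marrow for patients below 3 × 10^6 CD34+ cells/kg, but no step in the plan collects or stores marrow, and the same figure is a minimum in 6.4 and a goal in 6.22(e)

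*Combined protocol and SAP*

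**What the plan says.** Four places in the protocol bear on the graft.

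- **Section 6.4** requires at least 3 × 10^6/kg ("CD34 positive cells/kg will be collected with a target range of" 3 to 5 × 10^6/kg). The cells are "obtained by peripheral blood apheresis"; no marrow product is covered.
- **Section 6.22(e)** uses the same figure differently: "peripheral stem cells will be collected with the goal collecting" 3 × 10^6/kg. For a low yield it says: "If stem cell collections are poor the stem cell collection should then be delayed until the platelet count recovers", and it allows a higher G-CSF dose. It does not say what follows if the yield stays low.
- **Section 6.52, Day 0**, splits patients at 3 × 10^6/kg. Those at or above it fall under "CD34 cells/kg PSC's will receive PSC's only". For the rest: "All other patients will receive both primed PSC's and bone marrow". The handling text in the same paragraph covers one product: "The frozen peripheral blood cells will be transported to the transplant unit".
- **Section 7.0**, on reinfusion, discusses marrow as well as peripheral cells. It mentions DMSO given with the marrow and red-cell removal by Ficoll-Hypaque.

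Section 8.1 describes the regimen under study "as a preparative regimen for autologous BMT with primed peripheral stem cells". Sections 8.2 and 8.3 then estimate the engraftment rate and median time to engraftment, with no distinction by graft source.

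**The concern.** An instruction on the day of infusion can be carried out only if an earlier step has produced what it calls for. Here the order for marrow comes after busulfan, TBI and VP-16 have been given, and conditioning cannot be undone at that point. If the plan lets a patient arrive at Day 0 below the threshold, it should also say when that patient's marrow was collected and stored. If it does not let such a patient arrive, the second Day 0 branch should not be there.

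The statistical stake is smaller but real. Engraftment is one of the two rates whose precision justifies the sample size in 8.2. A pooled engraftment estimate could mix grafts of peripheral cells alone with marrow-supplemented grafts, and the supplemented patients would be those who mobilised worst. More than one centre takes part (6.4 refers to participating sites, and Appendix IIa gives a second centre's TBI schema), so sites could resolve the gap in different ways.

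**Working it through.** The point rests on reading the sections together. The plan has one related figure, the precision in 8.2, and it reproduces: the maximum standard error of a proportion at n = 50 is √(0.5 × 0.5 / 50) = 0.071, stated as 0.07. It shows that engraftment is a rate the trial was sized to estimate. It does not measure the size of this problem.

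**Step 1. Where could marrow come from?**

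| Place | Marrow collected or stored? |
|---|---|
| 6.21 (prior consolidation) | No; G-CSF primed cells only |
| 6.22(d)–(e) | No; G-CSF, apheresis, delay, higher G-CSF dose |
| 6.4 | No; cryopreservation of apheresis cells |
| 6.51 | No; diagnostic aspirate and biopsy only |
| Appendices III and IV | No harvest listed |
| 7.0 | Infusion and red-cell removal discussed; no time, patient group or collection step |
| 3.0 | A harvest is described, but in the 1989–1993 institutional series |

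**Step 2. Take each reading of the figure.**

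- *Binding minimum (6.4).* No patient reaches Day 0 below 3 × 10^6/kg. The second Day 0 branch is empty and its order has no function.
- *Goal (6.22(e)).* Some patients may reach Day 0 below it. The order then applies to them, but no step in the table supplies the marrow.

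Neither reading makes 6.4, 6.22(e) and Day 0 work together.

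**Step 3. Does anything intercept the second case?** In 6.52, busulfan resumes once pharmacokinetic results are known. Nothing in 6.51 or 6.52 refers to the stored CD34 dose or to stored marrow. The outcome in the second case is therefore possible under the text, though not certain.

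**Step 4. How many patients?** Only those still below the figure after the repeat collection in 6.22(e). No poor-collection rate is given. The earlier series in 3.0 transplanted 44 of 60 and 50 of 58 patients, so not all 50 accrued should be expected to reach Day 0, but those counts say nothing about CD34 yield.

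**Step 5. Which analyses are exposed?** The intent-to-treat analysis in 8.3 starts at consolidation, so a patient who drops out before transplant for low yield stays in it. The engraftment estimates and the subset followed from the day of transplant do depend on who is transplanted and with what.

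**The case against.** The best defence is that the plan contains a fallback that is merely under-described. Section 6.22(e) calls the figure a goal, Day 0 is the branch for patients who miss it, and 7.0 shows that the authors expected marrow to be infused and processed. The lead centre had harvested and frozen marrow in its earlier series. No sentence tells a site to begin conditioning without the product that Day 0 requires, and competent centres would check the graft first.

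Much of that stands. Marrow is anticipated, so the fault is a missing collection and storage step together with inconsistent wording of the figure. But an expectation in 7.0 does not say for whom, when or how marrow is obtained. The site procedures invoked in 6.4 concern cryopreservation of apheresis cells. The defence also leaves the minimum in 6.4 unexplained.

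Three stronger readings are tempting, and the documents do not support them:

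- *That the patient would be left without rescue.* Section 4.35(a) warns of fatal hypoplasia without marrow or stem cells. A patient with, say, 2 × 10^6/kg still receives those cells, and no engraftment threshold is given that would show rescue to be absent.
- *That efficacy would be distorted.* Intent-to-treat DFS retains patients dropped before transplant, and differences between sites are a possibility only.
- *That a definite share of the 50 patients is affected.* No figure in the documents supports one.

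**Conclusion.** The inconsistency holds. Sections 6.4, 6.22(e) and Day 0 cannot all be followed as written: either the Day 0 marrow group is empty, or a patient below 3 × 10^6/kg after repeat collection could finish conditioning with part of the ordered graft not collected. The number of such patients cannot be derived; repeat collection makes it smaller than the number with a poor first collection. For the results, the exposure is limited to the engraftment rate and time and the analyses counted from transplant.

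This rests on the text available. Appendices VI to XI were not in it. Section 13.0 identifies VI as the toxicity criteria, and the listed titles of 7 to 11 do not suggest a harvest procedure, but that could not be confirmed. A reader might go on to infer that the plan must make busulfan wait for a check of the graft. That would be a clinical rule for the sponsor to decide, and the inconsistency alone does not establish it.

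**What to change.** 1. Reconcile 6.4, 6.22(e), 7.0 and the Day 0 paragraph so that they agree on whether 3 × 10^6/kg is a minimum or a goal, and so that any product Day 0 can call for has a collection and storage step earlier in the plan. Which rule applies is the sponsor's decision.
2. Record the stored CD34 dose and the graft source for each patient. The transplant intake module listed as Appendix 11 may already capture this; if so, cite it.
3. If marrow-supplemented grafts remain allowed, report the 8.3 engraftment rate and median time with and without those patients. Intent-to-treat DFS needs no change.

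The cost is amendment wording, one data item and one descriptive split. If few patients receive supplemented grafts, the split will be imprecise and should be presented as description only.
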